4.0 Eligibility Criteria

4.1 Inclusion Criteria

- Male and female, between the ages of 18 to 35 years.
- Required to be a competitive recreational or college athlete and have at least 1-2 years of cycling or biking experience.
- Body Mass Index (BMI) of 18.5 to 28 kg/m²

- Considered “moderately to highly active” by the International Physical Activity Questionnaire (IPAQ).
- Have clinically treated mild to moderate persistent asthma and/or exercise-induced bronchoconstriction (EIB), with a resting forced expiratory volume in 1 second (FEV₁) > 65% of predicted.
- A ≥ 10% drop in FEV₁ after eucapnic voluntary hyperpnea (EVH).
- Prescribed short-acting β_2 -agonists (SABAs) by a physician.
- Comfortable not taking SABA before experimental visits.

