5.0 Study Design

The study design is a randomized, single-blind parallel group study. Participants will complete a formal screening visit and five experimental visits. The five experimental visits will occur each day ± 1 hour, at least 24 hours apart, and ≥ 2 hours postprandial.

The participants were required to visit the laboratory 5 times to complete the experimental tests. *Visit 1.* Participants underwent pulmonary function testing (PFT) and completed a eucapnic voluntary hyperpnea (EVH) challenge to diagnose EIB. *Visit 2.* Participants completed an incremental cycle ergometer test to determine VO_{2peak}. Male participants began with a 3-minute warm-up at 60W (61). After the warm-up, the test started at 100W and increased by 30W every minute until exhaustion (33, 61). A participant's VO_{2peak} was determined as the highest 30-second average VO₂ value (33, 61). All participants had a 1-hour rest period before the 16-km familiarization time-trial. *Visit 3.* Each participant completed two 8-minute constant-load exercise bouts, one at moderate intensity and another at submaximal intensity, and had a 1-hour rest period before the 16-km time-trial. After visit 3, participants were randomly assigned to either an IMT or a sham-IMT (control) group using a random number generator (1 = IMT, 2 = sham-IMT). Participants used a flow-resistive inspiratory muscle trainer (Pro2Fit, Smithfield, Rhode Island) in order to complete eight weeks of IMT, performed three times a week, prior to any exercise training that day. After 8 weeks of the IMT or Sham-IMT intervention, participants returned to the laboratory to repeat the PFTs, the EIB diagnosis via EVH, the familiarization time-trial, and the constant-load and performance time-trial post-IMT for *Visit 4* and *Visit 5*.

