8.0 Statistical Considerations

Data analysis was conducted using GraphPad Prism (GraphPad Software LLC, San Diego, CA, USA). All dependent variables were assessed for normality using the Shapiro-Wilk test, and corresponding Q-Q plots were visually inspected. When the assumption of normality was not met, a non-parametric Wilcoxon signed-rank test was performed. To evaluate main and interaction effects, a two-way repeated-measures ANOVA was performed for each outcome variable, with time (pre, post) and group (IMT, Sham-IMT) as within- and between-participants factors, respectively. When missing data precluded a full factorial ANOVA, a mixed-effects model with restricted maximum likelihood (REML) was used to account for unbalanced datasets and preserve statistical power. Significance was set at $p < 0.05$ for all comparisons. Data are reported as means \pm standard deviations (SD) and mean differences (MD) with 95% confidence intervals (CI).

A statistical power analysis was performed to estimate sample size using G*Power 3.1.9.7 (University of Kiel, University of Düsseldorf, and University of Mannheim, Germany). Utilizing F tests for ANOVA determined that 20 participants total (10 = IMT, 10 = Sham-IMT) are needed in the proposed study for a power of 0.80, with an effect size of 0.25 and an $\alpha = 0.05$. Based on previous work by Turner et al., (31), Duruturk et al., (46), Shei et al., (29), Hursh et al., (33), and Faghy et al., (82), standard parameters of $1-\beta = 0.8$ and $\alpha = 0.05$ are suggested. However, due to the limitation of participant recruitment, only 11 participants completed the study. Given the modest sample size, these findings should be interpreted as preliminary and hypothesis-generating. Given the modest and imbalanced sample size, statistical findings were interpreted with emphasis on effect sizes and 95% confidence intervals rather than sole reliance on p values. Interaction effects were considered the primary test of intervention efficacy, whereas within-group changes were interpreted descriptively to characterize response patterns. Non-significant findings were not interpreted as evidence of no effect but rather as inconclusive within the constraints of the present sample.

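### Efficacy is judged on unadjusted pre-to-post change; a baseline-adjusted estimate should stand beside it, chiefly to remove chance baseline imbalance in EIB severity

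*Combined protocol and SAP*

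**What the plan says.** Section 8.0 (Statistical Considerations) reports that "a two-way repeated-measures ANOVA was performed for each outcome variable, with time (pre, post) and group (IMT, Sham-IMT" as within- and between-participant factors. It adds that "Interaction effects were considered the primary test of intervention efficacy". No baseline covariate is named, either there or in the REML mixed model kept for missing data.

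Sections 2.1, 3.1 and 3.2 define the outcomes by values before and after training, so the covariate already exists. For EIB severity, the only pre-training EVH challenge that Section 5.0 lists is the one at Visit 1. That test also decides entry under Section 4.1: "A ≥ 10% drop in FEV₁ after eucapnic voluntary hyperpnea (EVH".

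On size, Section 8.0 says "Utilizing F tests for ANOVA determined that 20 participants total (10 = IMT, 10 = Sham-IMT" for power 0.80 at effect size 0.25, and then that "only 11 participants completed the study". It calls the sample imbalanced without giving the split. Section 5.0 describes assignment "using a random number generator (1 = IMT, 2 = sham-IMT".

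**The concern.** With one pre and one post value, the interaction F test is the square of a two-sample t test on change. Subtracting the whole baseline assumes that a participant who starts one unit higher would also finish one unit higher. Noisy measurements usually track less closely than that. When they do, an arm that starts worse by chance appears to improve more, whatever the training does.

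Arms of 10, and more so the handful per arm actually obtained, make a sizeable chance difference common. Section 8.0 asks readers to weigh effect sizes and confidence intervals above p values, so a shift in the point estimate falls on the very quantity the trial emphasises. Where the pre-post correlation is low, change scores also give up power.

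**Working it through.** **1. The plan's own sample size.** For the group-by-time interaction with 2 groups and m = 2 times, λ = f²·N·m/(1 − ρ) with 1 and N − 2 df. Effect size 0.25 is read as Cohen's f. It then equals a 1 SD difference in change, since four cells each deviate by 0.25 SD. At N = 20 and ρ = 0.73, λ = 0.0625 × 20 × 2/0.27 = 9.26 and power is 0.82. The N required for power 0.80 is 34 at ρ = 0.5, 22 at 0.7, 20 at 0.72–0.74 and 18 at 0.75. So the stated 20 is reached, within 2, only with ρ of about 0.70–0.75. That value is not stated in the document.

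**2. What the change score leaves behind.** Let d be the baseline difference between arms. Given d, the expected change-score estimate is effect + slope·d − d = effect − (1 − slope)·d. ANCOVA estimates the slope and removes this term on average.

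**3. How large d is likely to be.** In baseline SDs, SD(d) = √(1/n₁ + 1/n₂), with normal tails as an approximation:
- 10/10: √0.2 = 0.447; P(|d| > 0.5) = 0.26
- 6/5 (assumed): √(1/6 + 1/5) = 0.606; P = 0.41
- 7/4 (assumed): 0.627; P = 0.43

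**4. Size for the EVH drop.** Assumptions, none from the document: between-person SD 6–8 points, within-person SD 5, population mean drop 10–15, entry at 10 or more.
- Slope = 36/(36 + 25) = 0.59 to 64/(64 + 25) = 0.72, so 28–41% of d remains. Selecting on the baseline does not alter this slope.
- Baseline SD after selection is 4.7–6.6, against a post SD of 6.9–8.1.
- For d of half a baseline SD, the smallest case (mean 10, SD 8) gives 0.5 × 5.69 × 0.281 = 0.80 points. The largest (mean 15, SD 6) gives 0.5 × 5.66 × 0.410 = 1.16. That is roughly 0.10–0.16 post SD.

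**5. Precision with equal pre and post SDs.** Variances are proportional to 2(1 − ρ) for change and 1 − ρ² for ANCOVA, a ratio of (1 + ρ)/2. Estimating the slope multiplies the ANCOVA variance by 1 + 1/(N − 4). The two break even where (1 + ρ)/2 × [1 + 1/(N − 4)] = 1, which is ρ = 0.75 at N = 11 and 0.88 at N = 20. Counting the lost degree of freedom, expected CI widths break even at about 0.68 and 0.87. Simulated power, true effect 1 SD:

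| ρ | N=20 (10/10): change → ANCOVA | N=11 (6/5 assumed): change → ANCOVA |
|---|---|---|
| 0.3 | 0.43 → 0.58 | 0.24 → 0.30 |
| 0.5 | 0.56 → 0.66 | 0.31 → 0.35 |
| 0.7 | 0.78 → 0.81 | 0.48 → 0.48 |
| 0.9 | 0.997 → 0.996 | 0.91 → 0.88 |

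The assumed 7/4 and 8/3 splits show the same pattern.

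**6. Precision for the EVH drop.** The equal-SD table does not apply, because the entry rule shrinks the baseline SD. Residual variance is total × (1 − slope²) for ANCOVA, and that plus (1 − slope)² × baseline variance for change. For mean 10 and SD 6: 61 × (1 − 0.348) = 39.8 against 39.8 + 0.168 × 22.2 = 43.5, a ratio of 0.91. Across the scenarios the ratio is 0.88–0.94. The slope-estimation factor is 1 + 1/16 = 1.06 at N = 20 and 1 + 1/7 = 1.14 at N = 11, which uses up most or all of that. The simulated CI-width ratio (ANCOVA/change) is 0.97–1.00 at 10/10 and 1.01–1.05 at 6/5.

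**The case against.** The strongest defence is that nothing in the plan is invalid. The interaction test is unbiased over randomisation. Section 8.0 already labels the results preliminary and treats non-significance as inconclusive. The section was written after 11 people had finished, so replacing the primary analysis now would be a choice made with data in hand. If the sample size was set for the interaction, the implied correlation of about 0.70–0.75 is one where ANCOVA narrows the interval by only 4% at N = 20 and not at all at N = 11 (width ratios 0.96 and 1.01 at 0.73). All of this stands, and it limits the remedy to an added, labelled analysis.

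A reader might infer several stronger things that the documents do not support:
- *That ANCOVA is always more precise.* This is a large-sample result; step 5 shows where it fails.
- *That the 10% entry rule makes EIB severity the outcome with most power to gain.* Selection lowers the pre-post correlation, to 0.40–0.59 under the step 4 assumptions. It also shrinks the baseline SD and leaves the slope unchanged, so the gain nearly vanishes at N = 20 and reverses at N = 11.
- *That missing blocks cause the imbalance.* Section 5.0 mentions no blocks, but unstratified blocks would even out arm sizes, not baseline values.
- *That ANCOVA cures imbalance in general.* It adjusts only for the outcome's own baseline.

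What the defence does not answer is the conditional argument. Unbiasedness over all possible allocations does not help a reader of the one allocation that occurred.

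**Conclusion.** The point holds as an improvable choice of analysis, not an error. For EIB severity the case rests on conditional bias: 28–41% of any chance baseline difference stays in the estimate, or about 0.8–1.2 points of FEV₁ drop for a half-SD imbalance. It does not rest on precision there. For other outcomes a precision gain is possible: material at N = 20 if the correlation is 0.5 or below, modest at N = 11, absent at N = 11 above about 0.7, and a small loss at 0.9.

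The EVH figures depend on the assumed SDs, and the N = 11 figures on an assumed 6/5 split. The power figures assume a 1 SD effect and a range of correlations that the documents do not supply. The observed slope and baseline means would settle how much this matters in the actual data.

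**What to change.** For each pre/post outcome, and at least for EIB severity, report the IMT-minus-sham difference from an ANCOVA (post value on group plus pre value) with its 95% CI, beside the interaction result. Also report baseline means and SDs by arm and the observed pre-post slope, so that a reader can see how far the two estimates should differ. State that this analysis was added after data collection. In any continuation or successor trial, prespecify it as the primary analysis and state the correlation assumed in the sample size.

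The cost is one regression per outcome and one residual degree of freedom. At N = 11, expect slightly wider intervals for highly repeatable outcomes (about 5% at correlation 0.9) and for the EVH drop (1–5%).
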